1.5 Randomization

There is no planned randomization for this CPS.

1.6 Blinding

There is no blinding in this CPS.

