4.2.2.2 Nucleic Acid Amplification

- **Laboratory standard method (gold standard)**

Once the RNA has been extracted, each sample will be analysed by the gold standard (the laboratory standard PCR kit) to determine whether it is classified as positive or negative. In case the sample has already been analysed by PCR that result (Ct or copies/ml) must be used as reference.

- **Device under investigation**

Samples should be prepared as detailed in the IFU for PCR amplification. In the case of samples stored at -70°C, avoid repeated freeze-thaw cycles. The PCR amplification process is performed as detailed in Table 2. Prior to running the PCR, select the FAM and VIC channels to detect the SARS-CoV-2 genes *ORF1ab* and *N* respectively, and the Cy5 channel to detect the internal control gene RP. Amplification will be performed on a real-time multiplex PCR instrument with a readout in the FAM and VIC channels to detect both genes simultaneously and in the Cy5 channel to detect the internal control. In case the real-time PCR instrument requests a “Quencher dye” and/or “passive reference”, they must be set to “none”.

Table 2: PCR steps

STEPS	TEMPERATURE	REACTION TIME	CYCLES
Reverse Transcription	50°C	5 min	1
Pre-denaturation	95°C	30 s	1
Denaturation	95°C	5 s	45
PCR cycling	60°C	34 s	

For specific information about the interpretation of the results, please refer to the IFU. To consider the experiment as valid, each control in the kit should meet the requirements listed in Table 3.

Table 3: Results interpretation

	Positive Control	Negative Control
FAM channel (ORF1ab gene)	Ct ≤ 32	No Ct value or Ct>40
VIC channel (N gene)	Ct ≤ 32	No Ct value or Ct>40
Cy5 channel (internal standard gene)	Typical S-shaped curve, and Ct ≤ 32	No Ct value or Ct>40

If a typical S-shaped curve is observed after amplification in Cy5 channel of the specimen tested and Ct ≤ 38, the results can be determined as described in Table 4. For specimens tested as positive, when the Ct values of a target

gene are between 38-40, it is necessary to observe whether the amplification curve of the target gene is in sigmoidal shape. The suspected positive specimens should be verified (both amplification curves of FAM and VIC channels).

Table 4: Interpretation for test results

VIC channel \ FAM channel	Ct<=38	38<Ct<=40 (in a sigmoidal shape)	Ct>40
Ct<=38	Positive	Positive	Suspected Positive
38<Ct<=40 (in a sigmoidal shape)	Positive	Suspected Positive	Suspected Positive

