5.1.2 Specificity

The specificity of the SARS-CoV-2 NAD Kit is the ability to correctly classify specimens with no SARS-CoV-2 infection as negative (True Negative, TN).

To comply with the MDCG 2021-21 specificity will be assessed in 500 SARS-CoV-2 RNA negative human specimens defined so as to reflect the target population for which the device is intended, such as blood donors, hospitalised patients or pregnant women. These specimens must be confirmed in advance as a strong negative by the laboratory standard method.

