6. SELECTION OF SPECIMENS

6.1 Specimens and subjects providing specimens

The specimens used in this clinical performance study will be leftovers previously collected from male and female subjects suspected of SARS-CoV-2 infection through a nasopharyngeal swab. In this study, the requirement for informed consent may not apply or may be waived. If necessary, during sample collection, informed consent will be a general form to cover the use of the specimens in this clinical performance study. For further information about the informed consent process, see section 7.

The Principal Investigator or designee, previously trained in this CPSP, will revise specimens' eligibility according to the inclusion/exclusion criteria. Specimens meeting general inclusion criteria and no exclusion criteria shall be suitable to participate in the study.

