6.2 Eligibility criteria

The specimens must meet all of the inclusion criteria to be considered for the study. If any of the exclusion criteria are met, the specimen is excluded from the clinical performance study.

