6.2.1 Inclusion Criteria

- Specimen collected with a nasopharyngeal swab.
- Negative samples from specimens confirmed SARS-CoV-2 negative by the gold standard, or positive samples from specimens confirmed SARS-CoV-2 positive by the gold standard.

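### SAP 1.6 rules out blinding although some kit reads are visual and the opinion-based exclusion is not made final before the kit result; both estimates could be biased

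*SAP*

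**What the plan says.** On masking, SAP 1.6 reads "There is no blinding in this CPS", and CPSP 4.1 calls the study open-label.

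Reference status comes first. An inclusion criterion in CPSP 6.2.1 is "Negative samples from specimens confirmed SARS-CoV-2 negative by the gold standard", with a matching clause for positives. CPSP 5.1.2 adds for the negatives: "These specimens must be confirmed in advance as a strong negative by the laboratory standard method". Under CPSP 4.2.2.2, a PCR result that already exists serves as the reference.

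The kit read in CPSP 4.2.2.2 rests mostly on numeric Ct limits, with some curve inspection. CPSP Table 3 asks for an S-shaped Cy5 curve and Ct ≤ 32 in the positive control. A specimen's result is interpreted "If a typical S-shaped curve is observed after amplification in Cy5 channel of the specimen tested" and its Cy5 Ct is ≤ 38. For target Ct values between 38 and 40, "it is necessary to observe whether the amplification curve of the target gene is in sigmoidal shape". Suspected positives are then to be verified from both target-channel curves.

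On eligibility, CPSP 6.2 says "The specimens must meet all of the inclusion criteria to be considered for the study", and CPSP 6.1 says "Specimens meeting general inclusion criteria and no exclusion criteria shall be suitable to participate in the study". One exclusion in CPSP 6.2.2 rests on the investigator's opinion about contamination or deterioration. CPSP 4.2.2.1 also lets laboratory staff decide whether the RNA is suitable. SAP 2.1 defines one population, per protocol, as the specimens that meet the selection criteria, and SAP 2.3 uses it for the primary endpoint.

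**The concern.** A person who knows a specimen's reference status can settle a doubtful curve in line with the expected answer. The same knowledge could affect a Cy5 validity call, which removes a specimen from interpretation, or the positive-control read, which decides whether a whole run counts. Independently of curve reading, a specimen whose kit result disagrees with the reference could afterwards be judged deteriorated and so leave the per-protocol set.

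Both routes favour agreement, so any bias would plausibly raise sensitivity and specificity. The exact Clopper-Pearson intervals of SAP 2.2.1 cover sampling error only and would not reveal it. Appendix IV of the CPSP says that no performance thresholds are set, so the two estimates and their intervals are the whole result of the study.

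**Working it through.** **1. Plan's own figures.** SAP 2.4 gives 100 positives + 500 negatives = 600, which agrees. There is no expected error rate, threshold or share of borderline specimens, so the size of any bias cannot be computed from the documents.

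**2. What a shape read can change.** In CPSP Table 4, with the two target channels taken together:

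- both ≤ 38, or one ≤ 38 and the other 38-40 sigmoidal: Positive
- one ≤ 38 and the other > 40: Suspected Positive
- both 38-40 sigmoidal, or one 38-40 sigmoidal and the other > 40: Suspected Positive
- both > 40: Negative

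A non-sigmoidal curve at 38-40 has no cell. If it is treated like Ct > 40 (an assumption), one shape read moves Positive to Suspected Positive (≤ 38 with 38-40), or Suspected Positive to Negative (38-40 with > 40). No single shape read moves Positive to Negative. Neither document says whether Suspected Positive counts as positive, negative or neither in the 2x2 table, so the effect of a shape read depends on that undefined rule. If the final cell does change, one specimen moves sensitivity by 1/100 = 1.0 point or specificity by 1/500 = 0.2 point.

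**3. Timing of the opinion-based exclusion.** CPSP 6.1 and 6.2 place eligibility at entry. Neither section requires the decision to be dated, or bars revising it once the kit result is known. SAP Appendix A Table 2 lists unmet inclusion/exclusion criteria as a deviation type, so eligibility failures can surface after entry. SAP Appendix A Table 4 counts screening failures and completion, but not by reference status.

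**4. Illustration of late exclusion.** The error counts of 1, 2 and 5 per group are assumptions. For x correct calls out of n, the lower 95% Clopper-Pearson limit is the 2.5% quantile of Beta(x, n − x + 1). When x = n it is 0.025^(1/n); for example, 0.025^(1/99) = 0.963. Excluding k discordant specimens changes x/n to x/(n − k). Lower limits are in brackets.

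| Errors | Excluded | Sensitivity | Specificity |
|---|---|---|---|
| 1 | 1 | 99/100 = 99.0% (94.6) → 99/99 = 100% (96.3) | 499/500 = 99.8% (98.9) → 499/499 = 100% (99.3) |
| 2 | 1 | 98/100 = 98.0% (93.0) → 98/99 = 99.0% (94.5) | 498/500 = 99.6% (98.6) → 498/499 = 99.8% (98.9) |
| 2 | 2 | 98.0% (93.0) → 98/98 = 100% (96.3) | 99.6% (98.6) → 498/498 = 100% (99.3) |
| 5 | 1 | 95/100 = 95.0% (88.7) → 95/99 = 96.0% (90.0) | 495/500 = 99.0% (97.7) → 495/499 = 99.2% (98.0) |
| 5 | 5 | 95.0% (88.7) → 95/95 = 100% (96.2) | 99.0% (97.7) → 495/495 = 100% (99.3) |

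Excluding every discordant specimen is a worst case. With no kit errors this route has no upward effect.

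**The case against.** The strongest reply has four parts.

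*Most calls are numeric.* This stands. Target Ct values outside 38-40 need no shape read, and both Cy5 checks pair the curve shape with a numeric limit. The strong-negative requirement in CPSP 5.1.2 also suggests few borderline negatives, although SAP 1.4 asks only that they be confirmed negative. A reader might infer that kit calls are subjective in general; the documents do not support that.

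*Eligibility is settled at entry, and late changes leave a trace.* CPSP 6.1 and 6.2 do point to entry, and late exclusion is an inference rather than a planned step. CPSP 9.9 and SAP 2.10 analyse data as recorded, and both documents expect no drop-out. Case report forms for all specimens, the audit trail and deviation reporting (CPSP 10.5, 11 and 11.4) would make late removal traceable. They do not prevent it.

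*Nobody is shown to know the status while reading.* This is correct. One institution is both biobank and central laboratory, so a reader might infer that the same staff hold the status and read the curves. The documents do not say who reads them; such knowledge is possible, not stated.

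*Other documents may cover this.* The kit's instructions for use and the Data Management Plan were not available and may hold reading or lock rules. They would still have to be squared with the explicit statement in SAP 1.6.

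The open-label, retrospective design does not answer the point: stored specimens identified by a code (CPSP 11.1) lend themselves to masked reading.

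**Conclusion.** The point holds as a gap in bias control. Within these two documents, blinding is expressly ruled out, reference status precedes the kit run, four steps of the read include a visual judgement, and the opinion-based exclusion is not made final before the kit result although the only analysis set depends on it. Both estimates could be biased, plausibly upward.

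Two stronger conclusions are tempting and are not supported. The first is that bias will occur: nothing shows that a status-aware person will read curves or that specimens will be removed late. The second is that a study claim would pass or fail because of it: no threshold is pre-defined, so no stated margin is crossed.

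The size is unknown. The tabulated shifts rest on assumed error counts and assumed exclusions, and the effect of shape reads also depends on the undefined handling of Suspected Positive. The change should be made before testing, because bias from unmasked reads could not be removed afterwards.

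**What to change.** Replace SAP 1.6 and amend CPSP 4.2.2.2 to match:

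1. Kit curves, including the control curves of CPSP Table 3, are read by staff who see only a study code that does not reveal status. Positives and negatives are mixed on each plate. Run validity is decided before specimen calls are viewed.
2. Specimen-condition decisions (CPSP 6.2.2) and RNA-suitability decisions (CPSP 4.2.2.1) are recorded with date and reason before the kit run.
3. Kit calls, including Cy5 validity and verification of suspected positives, are locked in the EDC before the reference result is linked. Any discrepant resolution follows the lock. The discrepant-result provision in CPSP 4.2.2.2 must also be reconciled with SAP 1.3, which says that no comparison with the gold standard will be made.

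Amend SAP 2.1 so that no specimen leaves the analysis set on opinion after its kit result. In SAP Appendix A Table 4, count all post-run exclusions and invalid results by reason and reference status.

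Add a sensitivity analysis that restores any specimen excluded on opinion after a valid kit result, with the kit call it received. Report run-control failures and specimen Cy5 failures separately as invalid. Counting them as incorrect calls would not measure late-exclusion bias.

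The cost is a plate map, an EDC lock step, a table column and one extra analysis. This assumes that existing staff can separate holding the status from reading the kit, which the documents do not state. The sample size stays at 600, and no Ct limit changes.

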2. ANALYSIS CONSIDERATIONS

2.1 Analysis Populations

All specimens that meet the selection criteria are included in the per-protocol (PP) population, which will be analyzed as per the CPS Protocol (CPSP) and this Statistical Analysis Plan (SAP).

2.2 Statistical Methods

2.2.1 Descriptive statistics for categorical variables

For the categorical variables of sensitivity and specificity, results will be summarized with specimens counts and percentages/rates, and where specified in the table mockups, with exact 95% Clopper-Pearson confidence intervals.

2.2.2 Regression

No regression analyses are planned for this CPS.

2.3 Endpoint Analysis

The primary endpoint of this CPS evaluates the diagnostic accuracy of the SARS-CoV-2 Nucleic Acid Detection Kit in the diagnosis of COVID-19, which will be assessed through the definition of the sensitivity and specificity of the test:

- The sensitivity is the ability to detect a target marker (in this case, genetic material) associated with SARS-CoV-2. The sensitivity means the capacity to detect positive samples from COVID-19 patients. Therefore, sensitivity will be analyzed as the result of the ratio of the True Positive measurements (TP) to total known positive measurements (True Positive + False Negative).

$$\text{Sensitivity} = \frac{\text{True Positive}}{(\text{True Positive} + \text{False Negative})}$$

- The specificity is the ability to recognize the absence of a target marker (for this kit, genetic material), associated with SARS-CoV-2, which means the capacity to detect true negative samples of COVID-19. Consequently, specificity will be determined as the ratio of the True Negative measurements (TN) to total known negative measurements (True Negative + False Positive).

$$\text{Specificity} = \frac{\text{True Negative}}{(\text{True Negative} + \text{False Positive})}$$

The analysis of the primary endpoint will be performed using the PP population.

2.4 Sample Size Calculations

The sample size calculation is based on the purpose to determine the diagnostic accuracy (in terms of sensitivity and specificity) of the SARS-CoV-2 Nucleic Acid Detection Kit (Multiplex Real Time RT-PCR). According to the requirements defined in the MDCG2021-21, a total number of 600 samples is sufficient to prove these parameters, which will be divided considering different purposes:

- 100 positive samples of SARS-CoV-2 to test sensitivity.
- 500 negative samples of SARS-CoV-2 to test specificity.

No drop-out ratio is expected in this CPS.

2.5 Interim Analysis

No formal interim analyses are planned for this study. As such, no formal statistical rule for early termination of the investigation is defined. Interim study reports with descriptive analysis may be produced for regulatory or reimbursement purposes.

2.6 Learning Curve

No learning curve is required for the adequate evaluation of the primary endpoint of this CPS.

2.7 Timing of Analysis

The final analysis of the primary endpoints will be completed when all specimens have been analyzed by the investigational device.

2.8 Study/ Investigation Success

Success will be declared when the primary endpoint is met.

2.9 Subgroups of Analysis

No subgroup analyses are planned for this CPS. Nevertheless, stratification analyses according to different characteristics of the sample (viral load, storage time, freeze/thaw cycles, etc.) might be performed.

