1.1 Background and rationale

Corona viruses are a diverse group of viruses infecting many different animals causing mild to severe respiratory infections in humans. In 2002 and 2012, respectively, two highly pathogenic corona viruses with zoonotic origin, named as severe acute respiratory syndrome corona virus (SARS-CoV) and Middle East respiratory syndrome corona virus (MERS-CoV), emerged in humans and caused fatal respiratory illness, making outbreaks of corona viruses a new public health concern in the twenty-first century¹. This concern was confirmed in 2019 when a novel corona virus, designated as SARS-CoV-2 and associated with unusual viral pneumonia named Corona virus Disease 19 (COVID-19), sprouted in the city of Wuhan, China, and rapidly spread to create a global pandemic.

SARS-CoV-2 is a positive-sense single-stranded-RNA virus (+ssRNA), whose sequence is approximately 30,000 bases in length. As a novel beta-corona virus, it presents 79% genome sequence identity with SARS-CoV and 50% with MERS-CoV². Besides, its genome organization is shared with other beta-corona viruses, and the six functional open reading frames (ORFs) are arranged in order from 5' to 3': replicase (*ORF1a* and *ORF1b*), spike (*S*), envelope (*E*), membrane (*M*) and nucleocapsid (*N*). In addition, seven putative ORFs encoding accessory proteins are interspersed between the structural genes³.

Regarding the infectious capacity of SARS-CoV-2, any age group is susceptible to contagion, with a median age of infection around 50 years⁴⁻⁸.

The high transmissibility of SARS-CoV-2 may be attributed to its unique virological features. Transmission of SARS-CoV occurs mainly after illness onset and peaks following disease severity¹². However, the SARS-CoV-2 viral load in upper respiratory tract samples is highest during the first week of symptoms, and thus, the risk of pharyngeal virus shedding is very high at the beginning of the infection^{13,14}. This translates into a high transmissibility during mild disease or the asymptomatic period¹⁵.

Early diagnosis is crucial for controlling the spread of COVID-19 to minimize its impact on economic and health systems. The current diagnostic procedures for the identification of SARS-CoV-2-infected individuals are primarily based on three distinct approaches¹⁶:

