1. Immunological tests detect the host's immune response triggered by the virus through the detection of specific antibodies (IgM, IgG and IgA) directed against nucleocapsid (N) and spike (S) viral proteins¹⁶. Different types of assays can be used to determine different aspects of the adaptive immune response and functionality of antibodies.
2. Antigen tests are immunoassays that detect the presence of a specific viral antigen, which implies current viral infection.
3. Nucleic Acid Amplification Test (NAAT) is the gold standard method for diagnosis of COVID-19. NAATs for SARS-CoV-2 identify the RNA sequences that comprise the genetic material of the virus. This method

amplifies the virus' genetic material, if present. Amplification enables NAATs to detect very small amounts of SARS-CoV-2 RNA in a specimen, making these tests highly sensitive for COVID-19 detection.

NAATs can use different methods to amplify nucleic acids and detect the virus, and the detection time ranges from several minutes to hours depending on the technology^{21,22,24-26}. Currently, RT-PCR tests for COVID-19 are often based on specimens collected from the upper respiratory system using swabs. The first step to detect SARS-CoV-2 virus is the conversion of viral genomic RNA into DNA by a reverse transcriptase. This reaction relies on small DNA sequence primers designed to specifically recognize complementary sequences on the RNA viral genome, and on the reverse transcriptase to generate a short complementary DNA copy (cDNA) of the viral RNA. In real-time RT-PCR, the amplification of DNA is monitored as the PCR reaction progresses. This quantification is enabled by a fluorescent dye or a sequence-specific DNA probe labeled with a fluorescent molecule and a quencher molecule (e.g., TaqMan assays). An automated system repeats the amplification process for approximately 40 cycles until the viral cDNA can be detected by a fluorescent or electrical signal²⁷.

SARS-CoV-2 Nucleic Acid Detection Kit is presented as a method to detect covid cases in a short time as the procedure to obtain results only takes a little more than 6 min. In addition, this kit is intended to accurate the diagnosis of strong positives and strong negatives.

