2.2 Intended Use

TransGen SARS-CoV-2 Nucleic Acid Detection Kit is intended for *in vitro* qualitative detection of *ORF1ab* and *N* genes from the SARS-CoV-2 virus in nasopharyngeal swab specimens collected from COVID-19 suspected cases, suspected clusters of cases or other individuals who need SARS-CoV-2 infection diagnosis or differentiation diagnosis.

The definitions of COVID-19-related groups, such as “suspected cases” or “suspected clusters of cases”, are detailed in the Diagnosis and Treatment Protocol for Novel Corona virus Pneumonia, Surveillance Protocol for Novel Corona virus Pneumonia or other COVID-19 documents from the Centers for Disease Control and Prevention (CDC).

The TransGen SARS-CoV-2 Nucleic Acid Detection Kit should comply with the requirements of Diagnosis and Treatment Protocol for Novel Corona virus Pneumonia, Protocol for Prevention and Control of COVID-19 and other COVID-19 documents from the CDC. The biosafety requirements should be strictly followed as well.

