5.1.1 Sensitivity

The sensitivity of the SARS-CoV-2 NAD Kit is defined as the capacity to correctly detect confirmed positive specimens of SARS-CoV-2 infection (True Positive, TP).

To comply with the MDCG 2021-21, sensitivity will be assessed in 100 patient samples determined as SARS-CoV-2 RNA positive by the laboratory standard method (golden standard). So different SARS-CoV-2 genotypes/subtypes and mutants are considered, specimens from different stages (from 2020 to 2022) and outbreak clusters of the COVID19 pandemic will be selected from the biobank leftover material.

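### The 100 positives are chosen with no sampling method and no viral-load rule, and sensitivity by viral load is optional, so a set weighted to high-load specimens would comply and go unseen

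*SAP*

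**What the plan says.** SAP 2.4 fixes the denominator: "100 positive samples of SARS-CoV-2 to test sensitivity". Protocol 5.1.1 says that specimens from different pandemic periods and outbreak clusters "will be selected from the biobank leftover material". SAP 1.4 narrows the periods to three calendar windows, without a number per window. Protocol 6.2.1 asks only that a positive be a nasopharyngeal swab specimen confirmed positive by the reference PCR. The exclusions in 6.2.2 concern storage, freeze/thaw cycles and deterioration.

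On the reference result, Protocol 4.2.2.2 has each sample run on the laboratory's PCR after extraction, with this proviso: "In case the sample has already been analysed by PCR that result (Ct or copies/ml) must be used as reference". SAP 1.6 states that there is no blinding.

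On analysis, SAP 2.9 plans no subgroup analyses and then says that "stratification analyses according to different characteristics of the sample (viral load, storage time, freeze/thaw cycles, etc.) might be performed". Protocol 9.4 defers to the SAP. Appendix A of the SAP has one row for sensitivity, and its specimen table covers origin and storage temperature. SAP 1.3 rules out collecting or analysing additional data.

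The protocol's background (1.1) notes that "the SARS-CoV-2 viral load in upper respiratory tract samples is highest during the first week of symptoms". The intended use (2.2) covers "nasopharyngeal swab specimens collected from COVID-19 suspected cases, suspected clusters of cases or other individuals who need SARS-CoV-2 infection diagnosis".

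**The concern.** The sensitivity of an RT-PCR kit is not a single constant. It depends on how much target the specimens contain, and the kit's own reading rules (Protocol 4.2.2.2, Table 4) depend on Ct: above 40 in both channels is negative, and most weak combinations are only suspected positive. Missed and equivocal calls are therefore expected where signal is weak. The overall figure is an average over whatever viral-load mix the 100 positives have.

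The plan controls calendar period and outbreak cluster, which serve variant coverage. It does not control viral load, does not say how specimens are drawn within a period, and commits to no output showing the mix obtained. Two sites could follow the plan exactly, one taking mostly high-load tubes and the other a broad mix, and report different sensitivities with no way for a reader to see why. The planned Clopper-Pearson interval would not help, because it reflects binomial error for the specimens chosen and not how they were chosen. No performance threshold is pre-defined (Protocol Appendix IV), so the estimate and its interval are the study's main product and their interpretation is what is at stake.

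**Working it through.** **1. The plan's own figure.** 100 positives + 500 negatives = 600, as stated in SAP 2.4. The plan gives no expected sensitivity, precision, power or threshold from which to derive the split; it attributes the numbers to MDCG 2021-21. No stated number is disputed here.

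**2. What constrains viral load.**

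| Place | What it fixes | Viral-load rule? |
|---|---|---|
| Protocol 5.1.1, SAP 1.4 | period, outbreak cluster, RNA positive | none |
| Protocol 6.2.1, 6.2.2 | swab type, PCR status, storage, condition | none |
| Protocol 4.2.2.2 | earlier Ct or copies/ml used as reference if it exists | none |
| SAP 2.9 | stratification optional | no bands |
| SAP Appendix A | one sensitivity row | no Ct field |

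A high-load set breaches none of these, and none of the committed outputs would show it.

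**3. Sampling error for scale.** The exact 95% lower limit is the 0.025 quantile of Beta(x, n − x + 1). For x = 99 and n = 100 this is 94.6%. Distance below the estimate: 99.0 − 94.6 = 4.4 points.

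**4. Effect of the mix (assumed values).** The documents give no sensitivity by viral load and no Ct mix for the biobank. Let s be the low-load share:

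overall sensitivity = (1 − s) × Se_high + s × Se_low

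With Se_high = 99%:

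| Se_low | s = 0 | 10% | 20% | 30% | 40% |
|---|---|---|---|---|---|
| 60% | 99.0 | 95.1 | 91.2 | 87.3 | 83.4 |
| 80% | 99.0 | 97.1 | 95.2 | 93.3 | 91.4 |
| 90% | 99.0 | 98.1 | 97.2 | 96.3 | 95.4 |

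At s = 30% with Se_low = 80%: 0.70 × 99 + 0.30 × 80 = 69.3 + 24.0 = 93.3. The falls from 99.0 at s = 30% are 11.7, 5.7 and 2.7 points for Se_low of 60%, 80% and 90%.

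**5. When the mix outweighs sampling error.** The fall is s × (99 − Se_low). It passes 4.4 points when s exceeds 4.4/39 = 11%, 4.4/19 = 23% or 4.4/9 = 49% respectively. The effect is material in the first two cases at plausible shares, and small in the third unless low-load specimens are about half the set.

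**6. Precision of a band table.** Exact 95% intervals for a low-load band with 80% detected: 16/20 gives 56.3–94.3%, 24/30 gives 61.4–92.3%, 40/50 gives 66.3–90.0%. These are wide but adequate for a descriptive table.

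**The case against.** The strongest reply is that the plan already has selection structure (three windows plus outbreak clusters), ties the positives to MDCG 2021-21, and allows stratification by viral load. With no threshold set, a skewed mix cannot turn a numerical fail into a pass. The last point stands: this is a matter of interpretation, not of a pass/fail error. The windows and clusters are real but govern variants, not viral load. What the guidance requires on viral load cannot be seen from the documents, so it cannot be credited as filling the gap. Permission to stratify, without bands or commitment, leaves the analysis free to be omitted or its bands chosen late; SAP 2.9 does not say when that decision would be made.

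A reader might go further than the documents allow in four ways.

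- **That staff will hand-pick strong specimens.** The protocol says only that specimens will be selected; the method is unstated.
- **That the selector holds every specimen's Ct.** An earlier result is used only where one exists, may be in copies/ml, and need not be visible to whoever selects. Otherwise the reference PCR is run in the study.
- **That the background sentence "this kit is intended to accurate the diagnosis of strong positives and strong negatives" sets a selection rule.** It describes the kit. Where specimens are defined, Protocol 5.1.2 asks for strong results of negatives only, and Table 4 anticipates weak signals. A high-load set complies because the plan is silent on viral load, not because of this sentence.
- **That stage of infection drives the choice.** The stages named for selection are pandemic periods. Time since onset is not mentioned as a variable, and viral load is at best a proxy for it.

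**Conclusion.** The concern holds as a gap in sampling and reporting: the method of drawing the 100 positives is unspecified, viral load is unconstrained, and neither the reference Ct distribution nor sensitivity by viral load is a committed output. The plan permits a skewed set; nothing shows that one is intended or will occur.

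The size rests on assumed values. With low-load sensitivity between 60% and 90% and a 30% low-load share, the headline moves by 11.7 to 2.7 points, against 4.4 points of downward sampling error at 99/100. A reader might take a shift of about 8 points as the expected effect. That is one corner of the illustration (80% low-load sensitivity, 40% share: 99.0 − 91.4 = 7.6), and the documents support neither value. This should be changed because the remedy is cheap and the sensitivity estimate is hard to interpret without it.

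**What to change.** - **Protocol 5.1.1 and SAP 1.4.** Within each collection window, and within outbreak cluster where clusters are used, list all specimens meeting section 6.2. Take positives at random, or consecutively by collection date, until the target is reached, without using the reference Ct or copies/ml.
- **SAP 2.9 and Appendix A.** Replace the optional wording with a commitment to show the reference Ct distribution of the positives, and TP/N with exact 95% interval by reference Ct band. Fix the bands before the kit is run. Report specimens with copies/ml only separately. Overall sensitivity stays primary.
- **SAP 1.3.** Amend the bar on additional data so that the reference Ct or copies/ml is recorded for each positive.
- **Interpretation.** State that the draw reflects this biobank's mix, which may differ from the intended-use population. Random sampling from an archive removes choice by viral load; it does not make the archive representative.

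The sample size and primary endpoint are unchanged. The cost is wording in both documents, a listed draw, one table and perhaps one added CRF field. The headline sensitivity may be less favourable, and band intervals will be wide (24/30: 61.4–92.3%).
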